**After administration of study drug, the following post treatment procedures and assessments will be performed:**

- Vital sign measurements (sitting blood pressure, heart rate, respiratory rate, oral temperature): 30 minutes, 1 hour, and 2 hours following completion of the infusion; abnormal results to be repeated after 5 minutes of rest ([Section 6.5](#))
- Pulse oximetry: 30 minutes, 1 hour, and 2 hours following completion of the infusion ([Section 6.5](#))
- PK sample collection at 5 minutes, 1 and 2 hours after the completion of study drug infusion; record collection date and time for each PK sample ([Section 6.7](#))
- 12 Lead ECG (to be obtained in triplicate at 5 minutes after the completion of study drug infusion ([Section 6.6](#)))
- Concomitant medication assessment ([Section 6.10](#))
- AE assessment ([Section 6.9](#))

**7.2.3 Loading Doses 2 and 3 (Cohort 2 weekly Day 7 and 14 [±1 day])**

Subjects will return to the clinic for loading doses 2 and 3. Subjects should be encouraged to drink two 8-ounce glasses of water prior to dosing. The following procedures are to be performed prior to study drug infusion:

- Complete physical examination ([Section 6.3](#))
- Vital sign measurements (sitting blood pressure, heart rate, respiratory rate, oral temperature); to be measured immediately prior to the infusion ([Section 6.5](#))
- Pulse oximetry (to be measured immediately prior to the infusion) ([Section 6.5](#))
- Clinical safety laboratory tests (hematology, serum chemistry panel, urinalysis) ([Section 6.7](#))
- Immunogenicity sample collection (collected just prior to the start of study drug infusion) ([Section 6.7](#))
- PK sample collection (collected just prior to the start of the study drug infusion) ([Section 6.7](#))
- PD sample collection (collected just prior to the start of the study drug infusion) ([Section 6.7](#))
  - IgG, IgG subtypes (IgG1-4), IgA, IgM and CIC
  - Haptoglobin
  - Day 14 ONLY: Direct Coombs test
  - Day 14 ONLY: Quantitative Coombs assay
- Concomitant medication assessment ([Section 6.10](#))
- AE assessment ([Section 6.9](#))

**After the preceding procedures and assessments are completed:**

- Study drug administration (record date and time of dose of study drug) ([Section 9](#))

- Vital sign measurements (sitting blood pressure, heart rate, respiratory rate, oral temperature) will be performed at 15, 30, and 45 minutes after the start of the infusion and at completion of the infusion ([Section 6.5](#))
- Pulse oximetry will be measured at 15, 30, and 45 minutes after the start of the infusion and at completion of the infusion ([Section 6.5](#))
- Concomitant medication assessment ([Section 6.10](#))
- AE assessment ([Section 6.9](#))

**After administration of study drug, the following post treatment procedures and assessments will be performed:**

- Vital sign measurements (sitting blood pressure, heart rate, respiratory rate, oral temperature): 30 minutes, 1 hour, and 2 hours following completion of the infusion; abnormal results to be repeated after 5 minutes of rest ([Section 6.5](#))
- Pulse oximetry: 30 minutes, 1 hour, and 2 hours following completion of the infusion ([Section 6.5](#))
- Day 14 ONLY: 12 Lead ECG (to be obtained in triplicate at 5 minutes after the completion of study drug infusion ([Section 6.6](#)))
- PK sample collection at 5 minutes, 1 and 2 hours after the completion of study drug infusion; record collection date and time for each PK sample ([Section 6.7](#))
- Concomitant medication assessment ([Section 6.10](#))
- AE assessment ([Section 6.9](#))

**7.2.4 Maintenance Doses (Cohort 2 every other Week Day 28, 42, 56, and 70 [± 3 days])**

Subjects will return to the clinic for maintenance doses in Cohort 2 every other week dosing on Day 28, 42, 56, and 70. Subjects should be encouraged drink two 8-ounce glasses of water prior to dosing. The following procedures are to be performed prior to study drug infusion:

- Complete physical examination ([Section 6.3](#))
- Vital sign measurements (sitting blood pressure, heart rate, respiratory rate, oral temperature); to be measured immediately prior to the infusion ([Section 6.5](#))
- Pulse oximetry (to be measured immediately prior to the infusion) ([Section 6.5](#))
- Clinical safety laboratory tests (hematology, serum chemistry panel, urinalysis) ([Section 6.7](#))
- Day 28 ONLY: Pregnancy test ([Section 6.7](#))
- Day 28 ONLY: Serum tetanus antibody and VZV antibody ([Section 6.7](#))
- Immunogenicity sample collection (collected just prior to the start of study drug infusion) ([Section 6.7](#))
- Day 28 ONLY: PK sample collection (collected just prior to the start of the study drug infusion) ([Section 6.7](#))
- PD sample collection (collected just prior to the start of the study drug infusion) ([Section 6.7](#))
  - IgG, IgG subtypes (IgG1-4), IgA, IgM and CIC

- Haptoglobin
- Day 28 ONLY: Direct Coombs test
- Day 28 ONLY: D-dimer, antiphospholipid antibodies (lupus anticoagulant, anti-cardiolipin, and anti-beta-2-GP1 antibodies); antinuclear antibody titer; anti-double-stranded DNA antibody titer; complement component 3.
- Day 28 ONLY: Cold agglutinins (titer and thermal amplitude)
- Day 28 ONLY: Exploratory biomarkers (RNA seq)
- Day 28 ONLY: Quantitative Coombs assay
- Day 28 ONLY: Immune phenotyping by flow cytometry for measurement of CD3+CD4+ T, CD3+CD8+ T, monocytes, NK cells and B cells
- Concomitant medication assessment ([Section 6.10](#))
- AE assessment ([Section 6.9](#))

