- b. **Vital sign** measurements (sitting blood pressure, heart rate, respiratory rate, and oral temperature) to be obtained after 5 minutes of seated rest. Any abnormal measurements are to be repeated after 5 minutes of rest. Vital sign measurements will be taken on all study visits. On dosing days, vital sign measurements will be collected immediately prior to the infusion; 15, 30, and 45 minutes after the start of the infusion; at completion of the infusion; and 30 minutes, 1 hour and 2 hours following completion of the infusion.
- c. **Pulse oximetry**: On dosing day, pulse oximetry to be measured immediately prior to the infusion; 15, 30, and 45 minutes after the start of the infusion; at completion of the infusion; and 30 minutes, 1 hour, and 2 hours following completion of the infusion.
- d. **Clinical safety labs**: hematology, clinical chemistry, and urinalysis. See Section 6.7 for a complete list. Full clinical safety lab draws will be collected at screening and at all study visits prior to infusion if applicable. PD markers (albumin levels, hematocrit, hemoglobin, platelet count, reticulocyte count, lactate dehydrogenase, and total and indirect bilirubin) will be derived from the clinical safety laboratory results.
- e. **Pregnancy test (women of childbearing potential only)**: To be performed at time of screening and prior to dose on dosing days if applicable. Urine or serum test is acceptable; however, positive urine tests must be confirmed with serum testing.
- f. Digital 12-lead **ECG** to be obtained after 5 minutes of rest in the supine position and in triplicate approximately 1 minute apart. See Section 6.6 for additional information. On days of treatment, to be obtained 5 minutes after the completion of infusion.
- g. **Serology**: Any subject whose baseline value for tetanus or VZV was above the protective level at baseline and is not within 30% of the baseline value or is below the protective level by End of Follow-up, will be referred to their primary care physician for further management. See Section 6.7.3 for additional information.
- h. **PK**: Starting on dosing days, serum samples will be collected just prior to the start of study drug infusion (pre-dose) and at 5 minutes, 1 and 2 hours after the end of study drug infusion. See Section 6.7.4 for additional information.
- i. **Immunogenicity**: Samples will be collected pre-dose when collected on dosing days. See Section 6.7.6 for additional information.

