## **6. STUDY PROCEDURES**

### **6.1 Informed Consent**

All subjects must take part in the informed consent process. Adequate time must be allowed for the subject to ask questions and make a voluntary decision. No protocol-specific procedures, including screening procedures are to be performed until the subject has signed and dated an IRB-approved ICF. Subjects may withdraw consent at any time. Participation in the study may be terminated at any time without the subject's consent as determined by the Investigator.

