**After administration of study drug, the following post treatment procedures and assessments will be performed:**

- Vital sign measurements (sitting blood pressure, heart rate, respiratory rate, oral temperature): 30 minutes, 1 hour, and 2 hours following completion of the infusion; abnormal results to be repeated after 5 minutes of rest ([Section 6.5](#))
- Pulse oximetry: 30 minutes, 1 hour, and 2 hours following completion of the infusion ([Section 6.5](#))
- PK sample collection at 5 minutes, 1 and 2 hours after the completion of study drug infusion; record collection date and time for each PK sample ([Section 6.7](#))
- Concomitant medication assessment ([Section 6.10](#))
- AE assessment ([Section 6.9](#))

**7.2.6 Follow-up: Day 91, 112, and 140 ( $\pm 5$  days) (Day 91 is Early Termination [ET] Visit and Day 140 is End of Study [EOS] Visit)**

On Day 91, 112, and Day 140, subjects are to return to the clinic and the following procedures are to be performed.

*Note: If a subject prematurely discontinues study drug, the subject should be encouraged to attend, at a minimum, the early termination (ET) visit (Day 91), and subjects will also be encouraged to attend the remaining study visits (Days 112, and 140).*

*Subjects who prematurely discontinue from the study during follow up should attend the end of study (EOS) visit on Day 140.*

- Day 91 and 140 ONLY: Complete physical examination ([Section 6.3](#))
- Vital sign measurements (after 5 minutes of rest; sitting blood pressure, heart rate, respiratory rate, oral temperature): abnormal results to be repeated after 5 minutes of rest ([Section 6.5](#))
- Day 91 and 140 ONLY: Clinical safety laboratory tests (hematology, serum chemistry panel, urinalysis) ([Section 6.7](#))
- Day 91 and 140 ONLY: Pregnancy test ([Section 6.7](#))
- Day 91 and 140 ONLY: 12 Lead ECG ([Section 6.6](#))
- Day 91 and 140 ONLY: Serum tetanus antibody and VZV antibody See [Section 6.7.3](#) for additional information.
- Immunogenicity sample collection ([Section 6.7](#))
- PD sample collection ([Section 6.7](#))
  - IgG, IgG subtypes (IgG1-4), IgA, IgM and CIC
  - Haptoglobin
  - Day 91 and 140 ONLY: Direct Coombs test
  - Day 91 ONLY: D-dimer, antiphospholipid antibodies (lupus anticoagulant, anti-cardiolipin, and anti-beta-2-GP1 antibodies); antinuclear antibody titer; anti-double-stranded DNA antibody titer; complement component 3.
  - Day 91 and 140 ONLY: Cold agglutinins (titer and thermal amplitude)

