## **8. STUDY RULES**

### **8.1 Subject Withdrawal**

Every reasonable effort will be made to keep the subject in the study; however, if a subject withdraws from the study, the Investigator should complete and report the reasons for withdrawal as thoroughly as possible. The reason(s) for termination must be clearly documented on the appropriate page of the eCRF.

Subjects who have received at least one SYNT001 dose and withdraws or prematurely discontinue study drug should be encouraged to attend, at a minimum, the early termination (ET) visit (Day 112 for Cohort 1 or Day 91 for Cohort 2). Subjects in Cohort 2 will also be encouraged to attend the remaining follow up visits on Days 112, and 140.

If the subject fails to return for these assessments for unknown reasons, every effort (eg, telephone, email, and letter) should be made to contact them.

A subject's participation in the study may be prematurely discontinued for any of the following reasons:

1. The subject wishes to withdraw from the study.
2. Request by a regulatory agency or IRB.
3. Subject experiences a significant or intolerable AE.
4. The subject experiences a significant adverse change in vital signs, physical examination findings, or clinical laboratory parameter.
5. The subject has a need for a concomitant medication that is not permitted by the study protocol.
6. The subject experiences generalized impairment or mental incompetence that would result in the subject being unable to understand his or her participation in the study.
7. If, in the Investigator's medical judgment, further participation would be injurious to the health and well-being of the subject or is not in the best interest of the subject.
8. Administrative reasons, such as subject non-compliance or a major protocol violation.

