### 8.5.3 Individual Stopping Rule

Dosing for any individual subject will be discontinued (ie, further treatment with the study drug will not be given) if the subject experiences any study drug-related SAE or any study drug-related non-serious AE that, in the judgement of the Investigator (following consultation with Medical Monitor, if desired) suggests that it could be unsafe to administer further study drug to that subject.

Subjects who withdraw from this study due to an AE determined to be related to study drug are to be followed until there is:

- Resolution or stabilization of the AE determined to be related
- The subject is lost to follow-up
- The event is otherwise explained

If there is a persistent AE contributing to discontinuation that is determined to be related to SYNT001, subjects must be followed with appropriate medical management until resolution or stabilization.

Additionally, a subject will be discontinued from further treatment with study drug, at the discretion of the Investigator with consultation with the Medical Monitor, if they require a significant increase in doses of anti-WAIHA medications for the management of WAIHA.

If dosing with study drug is stopped because of an AE/SAE, or because of significant increase in doses of anti-WAIHA medications, or any other reason for prematurely discontinuation of study drug during the treatment period, the subject should be encouraged to attend, at a minimum, the ET visit (Day 112 for Cohort 1 or Day 91 for Cohort 2). Subjects in Cohort 2 will also be encouraged to attend the remaining follow up visits on Days 112, and 140.

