### **10.2 Adverse Event Definition**

An AE is defined as any untoward medical occurrence in a clinical trial subject associated with the use of a drug, whether considered drug related. An AE can be an unfavorable and unintended sign (eg, an abnormal laboratory value finding), a symptom, or a disease temporally associated with the use of a drug, without judgment as to causality. An AE can arise from use of the drug (eg, use in combination with another drug) and from any route of administration, formulation or dose, including an overdose. An AE also includes, but is not limited to, any clinically significant worsening of a pre-existing condition. Examples include:

- Any sign, symptom, physical finding, or laboratory result that has worsened in nature, severity or frequency compared to baseline;
- Reactions from an investigational drug, including those occurring because of an overdose, abuse of the study drug, withdrawal phenomena, sensitivity or toxicity;
- Concurrent illness that was not present or worsens in nature, severity, or frequency compared to baseline;
- Injury or accident; and/or
- Exacerbation of a pre-existing condition.

For data collection, all untoward events that occur after informed consent through the last study visit are to be recorded on eCRFs by the investigational site.

While pregnancy alone is not considered as an AE or SAE, any pregnancy complication(s) should be recorded as an AE(s) or SAE(s) (if applicable). Elective abortions without complications should not be regarded as AEs, unless they were therapeutic abortions (see below). Hospitalization for normal delivery of a healthy newborn should not be considered an SAE. If a female subject becomes pregnant during the conduct of the study, the Investigator must notify the Sponsor according to the procedures provided in [Section 10.3.8](#)).

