### **10.3.8 Reporting Pregnancies**

If a female subject or the female partner of a male subject becomes pregnant during the course of the study, the Investigator must report the pregnancy to the Medpace Safety using the **Pregnancy Reporting Form** within **24 hours** of becoming aware of the event. The Investigator must obtain consent to collect pregnancy information (including the status of the newborn, if applicable).

If some of the information required for completion of the Pregnancy Reporting Form is unavailable at the time of the initial report, follow-up reports will be completed and submitted within 24 hours of becoming aware of the new information. Any pregnancy will be followed through delivery for the observation of any SAEs. Any SAE that occurs during pregnancy must be recorded on the SAE report form in the electronic data capture (EDC) system (eg, maternal serious complications, therapeutic or spontaneous abortion, ectopic pregnancy, stillbirth, neonatal death, congenital abnormality, birth defect) and reported within 24 hours in accordance with the procedure for reporting SAEs (See [Section 10.3.9](#)).

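### Cohort 2 has one pregnancy test between first and last dose, so 4 of 8 infusions (9 of 13 on the weekly grid) follow it, and no stopping rule names pregnancy (minor)

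*Protocol*

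**What the plan says.** **Testing, every-other-week schedule.** Women of childbearing potential are tested at screening and before the first dose on Day 0. Section 7.2.4, which covers the infusions on Days 28, 42, 56 and 70, lists "Day 28 ONLY: Pregnancy test". Sections 7.2.3 (Days 7 and 14) and 7.2.5 (Day 84) list no test. Section 7.2.6 then gives "Day 91 and 140 ONLY: Pregnancy test". The Table 3 grid agrees with this text.

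**Testing, weekly schedule.** No part of Section 7 describes these visits. The grids (Protocol Table 10, SAP Table 4) mark screening and Days 0, 21, 91 and 140.

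**Footnote e.** In both Cohort 2 tables, in both documents, the footnote to the pregnancy row reads "To be performed at time of screening and prior to dose on dosing days if applicable".

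**Response to a pregnancy.** Section 8.5.3 ends a subject's dosing "if the subject experiences any study drug-related SAE or any study drug-related non-serious AE" judged to make further dosing unsafe, or for a significant increase in anti-WAIHA medication. Section 10.2 states "While pregnancy alone is not considered as an AE or SAE". The list in Section 8.1 opens with "participation in the study may be prematurely discontinued for any of the following reasons", and none of its 8 reasons names pregnancy. Under Section 10.3.8, if a subject "becomes pregnant during the course of the study, the Investigator must report the pregnancy"; this must be done within 24 hours, with follow-up through delivery. That section does not mention dosing.

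**Safeguards in place.** Inclusion criterion 9 requires a negative test before the first dose. Criterion 10 requires abstinence or two contraceptive methods through the final visit, with a failure rate below 1% per year.

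**The concern.** Cohort 2 has the longer treatment and may use the higher doses, yet its testing is sparse in the maintenance phase. A subject who conceives after the Day 28 test can receive all four remaining infusions before the next scheduled test on Day 91. If a pregnancy is found during dosing, by any route, the AE-based stopping rule does not apply to it, because pregnancy alone is defined as neither an AE nor an SAE. The site is told to report and follow the pregnancy. It is not told to withhold the next infusion. What is at stake is fetal exposure to study drug that a cheap test and one sentence would make less likely.

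**Working it through.** **Inputs.** Dose numbers come from Protocol Table 4 (Cohort Overview). Dose and test days come from Sections 7.2.1 to 7.2.6 and Table 3 (every other week) and from Table 10 (weekly). Visit windows are ±3 days on maintenance visits.

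**1. Reproduce the dose numbers.**
- Every other week: Days 0, 7, 14, 28, 42, 56, 70, 84 = 8, matching 3 + 5.
- Weekly: Days 0 to 84 in steps of 7 = 13, matching 3 + 10.

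**2. Infusions after the only test between first and last dose.** Infusions at visits later than the test visit are counted; the same-day infusion given after the test is not.

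| Schedule | Test | Later infusions | Count | Test to last infusion | With windows |
|---|---|---|---|---|---|
| Every other week | Day 28 | 42, 56, 70, 84 | 4 of 8 | 84 − 28 = 56 days | 87 − 25 = 62 days |
| Weekly (grids only) | Day 21 | 28, 35, …, 84 | 9 of 13 | 84 − 21 = 63 days | 87 − 18 = 69 days |

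**3. Internal benchmark.** Cohort 1 is tested on Day 0 and last dosed on Day 28 (Table 2), so its longest nominal test-to-infusion interval is 28 − 0 = 28 days. Cohort 2 allows 56 or 63 days, which is 2.0 or 2.25 times as long.

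**4. Footnote e against the grids.** Read as a test before every dose, the footnote contradicts the Day 28 restriction in Section 7.2.4, the absence of a test in Sections 7.2.3 and 7.2.5, and the blank cells in the grids. In Table 10 the PK footnote carries the same qualifier, and PK is marked on 5 of 13 dosing days (0, 7, 14, 21, 84). That favors reading the qualifier as *where marked*.

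**5. Effect of a Day 56 test.**
- Every other week (tests on Days 0, 28, 56): 42 − 28 = 14 days (windows 45 − 25 = 20), then 84 − 56 = 28 days (windows 87 − 53 = 34). Infusions after the last test: 70, 84 = 2 of 8.
- Weekly (tests on Days 0, 21, 56): 49 − 21 = 28 days (windows 52 − 18 = 34), then 84 − 56 = 28 days (windows 34). Infusions after the last test: 63, 70, 77, 84 = 4 of 13.

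**6. Size of the risk.** Expected conceptions = women × 0.01 per year × days/365. The documents do not give the number of women of childbearing potential, so 12 (upper bound) and 3 are assumed.
- From the last on-treatment test to the last infusion, 12 women: 12 × 0.01 × 56/365 = 0.018; weekly, 12 × 0.01 × 63/365 = 0.021.
- The part that a Day 56 test could catch, assuming instant detection, runs from the earlier test to Day 56: 28 days every other week, 35 days weekly.
  - 12 women: 12 × 0.01 × 28/365 = 0.009; 12 × 0.01 × 35/365 = 0.012.
  - 3 women: 3 × 0.01 × 28/365 = 0.002; 3 × 0.01 × 35/365 = 0.003.

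**The case against.** **Footnote e may already require more tests.** It can be read as a test before each dose. The PK comparison comes from Table 10; the Table 3 PK footnote lacks the qualifier. In the Table 3 safety-laboratory footnote the same qualifier seems to ask only whether an infusion takes place that day. Footnote e also omits Days 91 and 140, which the grid marks, so it does not simply mirror the grid. This stands as an ambiguity. It is sharpest on the weekly schedule, where no visit text settles it. It does not remove the point, because on the every-dose reading Section 7.2.4 and the grids would themselves be wrong.

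**Sites can already stop.** Section 6.1 says "Participation in the study may be terminated at any time" at the Investigator's determination, and reason 7 in Section 8.1 covers the subject's best interest. Reporting within 24 hours, with doses nominally at least a week apart, should normally alert the safety group before the next infusion. The consent form, Investigator's Brochure and Pharmacy Manual were not available, so a stop instruction there can be neither confirmed nor excluded. This largely stands: the missing sentence is a clarification. A reader might infer that the protocol keeps a pregnant subject on drug. The documents do not support that, since they permit stopping and only fail to require it.

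**Test frequency is a matter of preference.** The plan states no maximum interval, and every dosing visit includes a physical examination and AE assessment. This stands in part, but the 28-day interval is what the protocol achieves in Cohort 1.

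**The benefit is small.** This stands. Detection lag and the two-method requirement would lower the figures further. A reader might also add up the mg/kg given after the last test as a measure of harm. The protocol and SAP give no safety threshold against which to judge such a total.

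**Conclusion.** The point holds as a minor patient-safety improvement. On the every-other-week schedule, text and grid agree that 4 of 8 infusions follow the only test between first and last dose, by up to 56 days. The weekly figures, 9 of 13 and 63 days, are the grid reading only. Both intervals exceed the 28 days in Cohort 1. No stopping or withdrawal rule names pregnancy, so stopping rests on discretion.

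The expected benefit of a Day 56 test is at most about 0.009 to 0.012 conceptions caught with 12 women of childbearing potential, or 0.002 to 0.003 with 3. Both head counts are assumptions, and the rate is the ceiling in inclusion criterion 10. A reader might infer a substantial hazard, or that one added test closes the gap. Neither follows: the event is unlikely, and 2 of 8 or 4 of 13 infusions would still come after the last test. The case for acting is that the cost is very small and footnote e needs correcting on either reading.

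**What to change.** 1. Add a pre-dose urine pregnancy test on Day 56 to both Cohort 2 schedules (Section 7.2.4, Protocol Tables 3 and 10, SAP Tables 3 and 4). The longest test-to-infusion interval falls to 28 days nominal, 34 with windows.
2. Reword footnote e in all four tables to list the days: *Screening; before the dose on Days 0, 28 and 56 (weekly schedule: Days 0, 21 and 56), result known before infusion; and Days 91 and 140.* Section 6.7 sends pregnancy tests to the central laboratory and allows local retesting only for screening, so amend it to permit an on-site urine test. Otherwise a same-day result cannot be relied on.
3. As an accompanying clarification, add to Section 8.5.3, with cross-references in Sections 8.1 and 10.3.8: *Study drug is withheld after a positive urine test and permanently stopped once serum testing confirms pregnancy; safety follow-up continues.*

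Cost: at most 12 on-site urine tests for Day 56 (one per Cohort 2 subject, replacements aside), at a dosing visit where urine is already collected, plus a small change to Section 6.7. No visit, endpoint or analysis changes.
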